There has been intense interest in establishing whether the anabolic response to exercise can be enhanced by providing supplemental EAA (64-66). In normals, leucine-rich supplements are especially effective in promoting muscle protein synthesis and when combined with resistance exercise cause an even greater increase in muscle protein synthesis than exercise alone (64; 67). A similar response is seen with endurance exercise (68). Among commonly used protein supplements, whey is of special interest. It is readily digestible, is rich in EAA (~50g/100g/protein), particularly leucine (14g/100g), has a low Na, K, and phosphorus content, is inexpensive, and is effective in enhancing muscle protein synthesis (66; 69; 70). Hulmi (71) reported that whey acutely increased anabolic signaling in resistance exercise-trained normal subjects over 10.5 weeks. Regular exercise with whey supplementation caused a greater increase in muscle mass than exercise alone. Commonly a carbohydrate is added to the whey or AA supplement to stimulate insulin release and inhibit proteolysis induced by exercise (72). This combination also stimulates anabolic signaling induced by endurance exercise (68). Since in ESRD alterations in serum and intracellular AA profile with reduced serum BCAA levels are common (17; 23), provision of EAA at the time of exercise is likely to be especially effective. However, it is conceivable that there may be resistance to the signaling response to AA as there is for insulin/IGF-1 in CKD (50; 58). In healthy elderly subjects there is some impairment to AA-induced protein synthesis (73), and this can be overcome by increasing the leucine load (66), particularly in the form of whey protein (74). In a study with CKD rats, described below, we found that leucine alone largely corrects and stimulates the anabolic signaling defect present in these rats (30). Since leucine also stimulates protein synthesis in non-exercising humans including the elderly, it is recommended that the diet of the elderly include leucine-rich foods to prevent and treat sarcopenia (6; 75).

Specific Aims:

Specific Aim 1. To devise a safe, low-cost aerobic and resistance exercise regimen to counteract the loss of muscle mass and function common in elderly MHD patients that is easily implemented, suitable for the home and to which most subjects will adhere.

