Group Assignment. After screening and baseline testing, an independent third party investigator ([name], letter attached) will *match MHD subjects on age, body mass index (BMI), MHD duration, and protein intake*, and assign them randomly to the exercise or usual care study groups. At the end of 12 weeks of study this investigator will assign half of the subjects in each group to receive a blinded nutritional supplement (high calorie whey or placebo). The blind will be broken on completion of the study.

Dietary Control. Prior to entry into the study the subjects will be encouraged to consume 1.2 g protein/kg/day, per Kidney Disease Outcomes Quality Initiative (KDOQI) recommendations (92) and advised to maintain a steady intake. However, we realize that the recommended intake may not be achieved in some subjects. In order to adjust for variation in protein intake we will measure the subject's protein intake on 3 occasions during the month prior to entry into the study. Then when assigning subjects to the study groups, measured protein intake will be taken into account by the third part study assigner, so that the protein intake in the 2 study groups will be similar. Protein intake will be monitored by three-day dietary records and the normalized protein equivalent of nitrogen appearance (nPNA), a reflection of protein intake in stable conditions. nPNA is calculated from the urea generation rate by means of kinetic modeling using measurements of pre- and post-dialysis urea levels plus any urea lost in the urine in patients with residual renal function. After entry into the study nPNA is calculated weekly for the first two study weeks, then monthly. During the study period, there will be regular bi-weekly follow up counseling by a dietitian in an effort to ensure that both groups meet target dietary protein intakes

Safety Measures. Before screening, subjects will be informed of the nature of the study and the procedures to be performed, and will sign an approved consent form. Measures to monitor and ensure safety include a screening ECG, maximal exercise test, and medical approval (see screening). The cardiovascular exercise lab has extensive experience in conducting clinical studies and has a staff of experienced personnel. We do not expect any long-term side effects from the proposed interventions. The exercise program is well balanced and varied with aspects of strength and aerobic training. Subjects will

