Since this is a pilot sub-study carried out with a limited number of subjects after completion of the main 12 week study, we have adopted a unilateral exercise protocol in which the resting contralateral limb serves as a control. This protocol will allow us to gain considerable insight into the salutary molecular processes activated by exercise in ESRD subjects and to test whether these processes can be enhanced by provision of a leucine-rich supplement. In brief, two to three days after completing the primary 12-week study, subjects from both the exercise and usual care groups will be studied in which one limb is exercised for 15 minutes, after which the vastus lateralis muscles of both the exercised and the contralateral resting limb will be biopsied. *Half the subjects in each of these 2 main groups (12 subjects from each group) will be matched by BMI and age and randomized to either a placebo mixture or a high calorie nutrient supplement.* The nutrient supplement will consist of a high-calorie leucine-rich protein (whey protein) given at the start and end of the exercise session. The study consists of the following 4 groups, each undergoing acute, unilateral exercise:

- Group 1.** Regular exercise group plus placebo
- Group 2.** Regular exercise group plus nutrient supplement
- Group 3.** Usual care group plus placebo
- Group 4.** Usual care group plus nutrient supplement

An outline of the experimental protocol is illustrated in Figure 2, and a detailed protocol follows.

[figure not shown]
Figure 2. Acute Exercise, Muscle Biopsy, and Nutrient Supplement Protocol for Specific Aim 2

Biopsies will be obtained from the dominant limb after acute exercise and from the non-dominant limb following rest. A *single* biopsy of each limb will be taken from each subject. Tissue taken from the biopsies will undergo molecular analysis to answer the following questions:

[figure not shown]

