3. Does ingestion of a high-calorie leucine-rich protein (whey) supplement enhance acute exercise-stimulated anabolic signaling? (Specific Aim 2A). The effect of a nutritional supplement on acute exercise-induced signal transduction will be assessed by comparing IRS-1/AKT and mTOR signaling in a unilateral acutely exercised limb of regularly exercised subjects ingesting the supplement (Group 2) versus the acutely exercised limb of comparable subjects ingesting placebo (Group 1). A similar comparison will be made between the exercised limbs of usual care subjects ingesting the supplement (Group 4) versus placebo (Group 3) (Fig 5).

We anticipate that the leucine-rich supplement will enhance the acute exercise-stimulated mTOR signaling pathway and that the response will be more marked in the group undergoing the 12 week exercise program. This thesis is based on reports that in healthy young subjects, a leucine-rich supplement added to a resistance exercise program stimulates muscle protein synthesis, mass and strength (64; 72) and although delayed in the elderly, the anabolic response is effectively stimulated by this regimen (73). In this regard, Hulmi reported that whey protein enhanced exercise-induced signal transduction (phosphorylation of p70S6K) by nearly five-fold over exercise alone in young healthy subjects (71).

Figure 5. Assessment of the effect of nutrient supplementation on the response to acute exercise.

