The unilateral exercise will be performed using seated single knee extension exercise against resistance. Subjects will be seated with the hips flexed at 90° with their back against a backrest at a ≈110° angle. The leg pad will be positioned ≈5 cm above the ankle and the rotation arm will be positioned so that the knee is bent to 90°. After a warm-up consisting of 8-10 repetitions with minimal resistance, the weight will be adjusted to 70% of the one repetition maximum. The unilateral 1-RM will be determined by a post-training period strength test, performed on a different day. Five sets of 10 repetitions will be performed, with 2 minutes of rest periods between sets. The load will be adjusted during the course of the session due to fatigue such that each subject is able to perform 10 repetitions during each set.

The supplement, high-calorie whey, (300 ml) comprises 24 g whey protein (contains ≈3 g leucine) with 30g carbohydrates (sucrose) in liquid, and the placebo contains a liquid, dextrose 24 g plus sucrose 30g. The amount of whey (Nestle Healthcare) prescribed is guided by studies in normal subjects (66; 69; 70; 110) including the elderly (70; 74). We do not anticipate any adverse effects from nutrient or placebo if taken as prescribed. Whey has a low NA, K and phosphorus content (60,140 and 60 mg/serving respectively). The vehicle for dissolving the powdered supplement will be of the subject's choice, but is limited to fluids permissible for ESRD such as apple juice and will be pre-tested for taste by the subject. Whey is also available in a variety of flavors and in long term studies has been included in baked goods or sprinkled over foods.

Detailed molecular analysis of skeletal muscle. The following items will be measured using methods established in [name] laboratory. Note that receptor and signaling proteins will be measured by western immunoblots; mRNA levels by real-time quantitative PCR, and selected degradative proteins by immunoblotting and serum and local IGF-1 by ELISA.

- mRNA levels of local regulators of muscle mass: Total IGF-1 (all transcripts), the Ea transcript (a generalized tissue form and main form in liver, and the IGF-1Eb transcript, MGF, a loading sensitive and more potent form than the Ea form). Myostatin, and receptors for IGF-1, insulin, growth hormone and androgens.
- mRNA levels of inflammatory cytokines IL-6 and TNF α .

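### Each subject chooses the fluid for the whey or placebo powder and it is not recorded, so carbohydrate intake can vary by an amount comparable with the 24 g difference between the drinks

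*Combined protocol and SAP*

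**What the plan says.** The drinks are defined in the Detailed Protocol for Nutrient Supplementation, Acute Exercise, and Biopsy for Specific Aim 2. For the active drink: "The supplement, high-calorie whey, (300 ml) comprises 24 g whey protein (contains ≈3 g leucine) with 30g carbohydrates (sucrose) in liquid". For the comparator: "the placebo contains a liquid, dextrose 24 g plus sucrose 30g". The same paragraph continues: "The vehicle for dissolving the powdered supplement will be of the subject's choice, but is limited to fluids permissible for ESRD". Apple juice is the example given, and each subject tries the drink for taste beforehand. Half the drink is taken at the start of the exercise and half at the end, and both limbs are biopsied after a further 60 minutes of rest.

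I read the vehicle sentence as covering both arms, because Group Assignment uses the word supplement for both products: a third party will "assign half of the subjects in each group to receive a blinded nutritional supplement (high calorie whey or placebo"). The sub-study description adds: "Half the subjects in each of these 2 main groups (12 subjects from each group) will be matched by BMI and age and randomized".

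On why sugar matters, Background and Significance says: "Commonly a carbohydrate is added to the whey or AA supplement to stimulate insulin release and inhibit proteolysis induced by exercise". The molecular analysis section lists IRS-1, Akt, mTOR, p70S6K, rpS6 and 4EBP-1 as signaling proteins activated by, among other things, insulin.

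Three comparisons of whey with placebo are described:
- Question 3 of the approach to Specific Aim 2 compares exercised limbs between subjects: "comparing IRS-1/AKT and mTOR signaling in a unilateral acutely exercised limb of regularly exercised subjects ingesting the supplement (Group 2") against Group 1, and likewise Group 4 against Group 3.
- Secondary analyses, Specific Aim 2A, defines a change measure, exercised limb minus resting limb in the same subject.
- The same section adds a comparison of supplement with placebo in the resting limb.

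**The concern.** The session is otherwise tightly controlled: a light protein-free breakfast, a fixed interval and a rest period before exercise. Yet a possible sugar load is left to the subject within the last hour or so before biopsy. On the plan's own account, sugar releases insulin and insulin activates the pathway being measured.

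Two consequences follow. First, vehicle sugar adds between-subject variation to a pilot contrast that has few subjects and no power calculation. Second, whey and dextrose may well taste different, and the plan does not say which product is tasted or whether the fluid is chosen before allocation. If the choice follows the product, part of a whey-placebo difference in signaling would come from the fluid.

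The written procedure mentions no insulin or glucose sample at this session; the HOMA-IR samples are fasting ones at 0, 6 and 12 weeks. An unrecorded vehicle could not be allowed for afterwards. A positive pilot is meant to found a larger study, so a clean contrast has value.

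**Working it through.** The documents give no sample size or power figure for the Aim 2A contrast, so there is nothing of that kind to reproduce.

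**Inputs from the documents.** Whey drink: 24 g whey protein, 30 g sucrose, 300 ml. Placebo: 24 g dextrose, 30 g sucrose. Cell size: 6 or 12, because the sub-study wording allows either reading.

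**Assumptions.** Sugar content of the juice, volume of vehicle, and that the stated sugar excludes the vehicle.

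**Step 1, planned difference.** Placebo carbohydrate is 24 + 30 = 54 g; whey drink carbohydrate is 30 g; difference 54 - 30 = 24 g, placebo higher.

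**Step 2, sugar added by the vehicle.** Added grams = concentration (g/100 ml) × volume (ml) / 100.

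| Juice, g/100 ml | 150 ml | 200 ml | 240 ml | 300 ml |
|---|---|---|---|---|
| 5 | 7.5 | 10 | 12 | 15 |
| 8 | 12 | 16 | 19.2 | 24 |
| 10 | 15 | 20 | 24 | 30 |
| 12 | 18 | 24 | 28.8 | 36 |

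The range is 7.5 to 36 g, against 0 g for a sugar-free fluid.

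**Step 3, break-even.** The vehicle adds more than 24 g when concentration exceeds 24 / volume × 100: above 8 g/100 ml at 300 ml, 10 at 240 ml, 12 at 200 ml, 16 at 150 ml.

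**Step 4, chance imbalance between arms.** Suppose each subject independently takes juice with probability 0.5, and juice adds 33 g (11 g/100 ml × 300 ml). The SD per subject is 33 × 0.5 = 16.5 g. The SE of the between-arm difference in mean vehicle sugar is 16.5 × √(2/n). Probabilities are from exact binomial enumeration.

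| Subjects per cell | SE | P(imbalance ≥ 12 g) | P(imbalance ≥ 24 g) |
|---|---|---|---|
| 6 | 9.5 g | 14.6% | 0.6% |
| 12 | 6.7 g | 6.4% | 0.03% |

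The 12 g threshold is half the planned difference. The result is sensitive to the assumed load: at 15 g per juice drink, P(≥ 12 g) is 0.6% with 6 per cell and about zero with 12; at 36 g it is 38.8% and 15.2%.

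**Step 5, choice that depends on the product.** If 80% took juice with whey and 40% with placebo (illustrative only), the expected shift at 33 g is 33 × (0.8 - 0.4) = 13.2 g, and the planned gap shrinks to 24 - 13.2 = 10.8 g. At 70% against 50% the shift is 33 × 0.2 = 6.6 g and the gap is 17.4 g.

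**Step 6, which contrasts are exposed.** The direct exercised-limb and resting-limb comparisons are between subjects and carry the whole vehicle effect. The exercised-minus-resting measure removes the part of a systemic insulin effect that is common to both limbs, and no more.

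**The case against.** A reader might infer that carbohydrate varies by more than the planned difference, and that this confounds the contrast. The documents support neither as a plain statement.

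- **Size.** They give no sugar content for juice and no volume of added fluid. The 30 g could describe the finished drink; the plan mentions no adjustment of the sucrose to the fluid chosen, but the wording leaves this open. At 150 ml the vehicle stays below 24 g throughout the range tabulated.
- **Confounding.** Assignment is randomized and blinded. A free choice within randomized arms gives variance and chance imbalance. Bias needs the choice to depend on the product, which the taste test makes possible but nothing shows. An arm-level imbalance as large as 24 g is improbable under random choice.
- **Yardstick.** The 24 g gap is not the contrast under test: dextrose replaces whey gram for gram. The question is whey against no whey, which no vehicle alters. The effect of extra sugar on the signaling readouts is not quantified.
- **Inference.** The plan asks about a high-calorie protein supplement and concedes, in limitation 8, that no specific amino acid can be credited. It also says amino acids themselves raise insulin.
- **Protection.** The limb difference may be the intended operational form of the exercised-limb comparison, in which case that comparison is partly protected.

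These points stand and set the limits of the finding. They do not explain why the fluid should be left free and unrecorded, and limitation 8 does not mention vehicle sugar.

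**Conclusion.** The point holds as a cheap improvement to a pilot aim. The vehicle is neither standardized nor, in the text, recorded or adjusted for, and under the stated assumptions it adds about 8-36 g of sugar, comparable with the 24 g difference between the drinks. Exceeding 24 g is conditional on concentration, volume and the stated sugar excluding the vehicle. The supportable consequence is added noise and a risk of chance imbalance in cells of 6 or 12. Bias is possible only if the choice depends on the assigned product. The resting-limb comparison is fully exposed, as is the exercised-limb comparison when made directly; the limb difference is partly protected. Nothing here touches peak VO2 or the main randomized comparison.

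**What to change.** Replace the subject-chosen vehicle with one common vehicle and one volume for all subjects in both arms, selected by the study team from the permitted fluids. The between-subject range from the vehicle is then 0 g and the carbohydrate difference is the planned 24 g.

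If a choice must stay, have it made before the supplement is allocated, record type and volume, and state in the statistical analysis plan that the Aim 2A comparisons are adjusted for it. The protocol should also say whether the stated grams of sugar include the vehicle.

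The cost is a sentence or two in the sub-study procedure and possibly a slightly less palatable single drink. The second option also needs one more recorded item and uses a covariate in very small cells, so the common vehicle is preferable.

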Primary endpoint, Specific Aim 1. For this analysis we have used data from a recent 12-week study by Storer et al (36) on the effects of endurance exercise versus no exercise (usual care) on cardiorespiratory and skeletal muscle function in MHD patients. Change from baseline for peak VO₂ was 22% (an increase) in the exercise group and 6% (a decrease) in the usual care group. These findings are consistent with an average increase from baseline of 17% in MHD patients participating in exercise-based rehabilitation programs reported in the literature (14). Similarly, our primary outcome will be comparison of the change in peak VO₂ for patients randomized to exercise vs. usual care. To calculate the desired sample size we used a two group t-test of equal means and calculated the per group sample size (East 5, Cytel Inc, copyright 2007). Given the desired values for the standardized effect size (the absolute value of the difference in group mean changes divided by the common standard deviation) and overall level of significance and power of the test, the required sample was calculated. To detect a difference in group mean changes of 17% in peak VO₂ for exercise vs. usual care, given a common standard deviation of 20% (based on Storer et al (36), using a standardized effect size of 0.85), 23 subjects/group would be required to complete the study to achieve statistical power of 80% with a two-sided test of significance at the 0.05 level. Appendix VII shows how the required sample size varies by the standardized effect size for power of 0.80 (solid curve) and 0.85 (dashed curve). Appendix VIII provides curves showing how the power varies by the standardized effect size for a per group sample size of 23 (solid curve) and 26 (dashed curve). For example, a per group sample of 23 provides power of about 0.17 and 0.38 to detect a small (0.3) and medium (0.5) standardized effect size, respectively. To allow for a 20% dropout rate we plan to enroll 30 subjects per group, or a total of 60. The 20% dropout rate is based on the PI's experience (87), and other similar research studies.

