Statistical analysis plan. Comparisons of clinical and demographic data between groups at baseline will be performed by the appropriate statistical test (for continuous variables, t-test for normally distributed data and Wilcoxon test for non-normal data; for categorical variables, chi-square test or Fisher's exact test). These comparisons will be performed at baseline only to assess adequacy of randomization. Comparisons between groups for cardiopulmonary exercise test, muscle biopsy, energy expenditure, cognitive function, and other functional measures before and after the study period will be performed by multivariate ANOVA; post-hoc comparisons will be made using the Bonferroni method. To analyze continuous variables measured at three or more time points we will use linear mixed effects regression (114). To explore the relationships between a given outcome and other variables, we will use multiple regression techniques. Since the reliability of a fitted regression model may be reduced if too many predictors are used (114), we will limit the number of predictors to four variables in each model ($\leq 1/10$ of the total). For the primary outcome, change in peak VO_2 , the specific independent variables in the model will include exercise compliance (average energy expended in kcals/week), change in muscle strength, and change in muscle mass. Missing data will be managed using the multiple imputation method which is preferable to older methods and described in detail by Schafer & Olsen (1999).

For Specific Aim 2 (effect of acute and chronic exercise on muscle wasting), we will employ a linear model, using period (baseline vs. 4 months) and treatment (exercise training vs. usual care) as independent variables along with their interaction (Bonferroni method). The intention to treat principal will be applied for all analyses.

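### The primary comparison of change in peak VO2 names no baseline covariate and fixes no analysis scale; this is a possible, conditional loss of efficiency, not an error

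*Combined protocol and SAP*

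**What the plan says.** Under Statistics, Primary endpoint, Specific Aim 1, the plan says: "Similarly, our primary outcome will be comparison of the change in peak" VO2 for exercise against usual care. The sizing follows from that: "To calculate the desired sample size we used a two group t-test of equal means". The target is a 17% difference in mean change, "given a common standard deviation of 20" percent, which is a standardized effect of 0.85. The result is 23 completers per group for 80% power at two-sided 0.05, and then: "To allow for a 20% dropout rate we plan to enroll 30 subjects per group".

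Under Statistical analysis plan, between-group comparisons of the cardiopulmonary exercise test "before and after the study period will be performed by multivariate ANOVA", with no covariate named. A later sentence, beginning "To explore the relationships between a given outcome and other variables", introduces multiple regression, for which "we will limit the number of predictors to four variables in each model". For change in peak VO2 the variables listed are exercise compliance in kcal/week, "change in muscle strength, and change in muscle mass". Neither group nor baseline peak VO2 is in that list.

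Peak VO2 is measured in Part 2 of Screening, and Group Assignment takes place after screening and baseline testing. The Inclusion criteria require 10 to 20 ml/kg/min. The matching factors are age, BMI, dialysis duration and protein intake; baseline peak VO2 is not one of them.

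**The concern.** Two things are left open.

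First, baseline peak VO2 is used neither in the allocation nor in the primary comparison. With two time points and complete data, the group-by-time test in a before-and-after ANOVA is the same test as the t-test on change, so the multivariate ANOVA supplies no adjustment. The regression named for this outcome does not supply it either. Its variables arise after randomization, so it cannot stand in for the randomized comparison.

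Second, the scale is not stated. The percent figures in the sizing suggest percent change, but nothing says whether the analysis uses percent change, change in ml/kg/min or the 12-week value. With a t-test in one section, multivariate ANOVA in another and no stated scale, the choice stays open after the data are seen.

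What is at stake is efficiency and prespecification. Validity is not in question: comparing change scores between randomized groups is unbiased.

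**Working it through.** **1. The plan's own figure.** For a two-sample t-test with d = 17/20 = 0.85, two-sided 0.05, using the noncentral t:

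- 22 per group: 0.786
- 23 per group: 0.805, so the stated 23 reproduces
- 24 per group (30 enrolled, 20% dropout): 0.822
- 30 per group, all observed: 0.899

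The plan's quoted powers at 23 per group for effects of 0.3 and 0.5 SD (0.17 and 0.38) also reproduce, at 0.169 and 0.382.

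**2. Assumptions needed for the adjusted analysis (none is in the documents).**

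- Mean baseline 15 ml/kg/min, so SD of change = 0.20 × 15 = 3 and effect = 0.17 × 15 = 2.55.
- Baseline SD 2.0, 2.5 or 2.89. The last is a uniform spread over the 10–20 entry range: 10/√12 = 2.89.
- Within-group slope b of the 12-week value on baseline, from 0.5 to 1.

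**3. Formula.** Change has slope b − 1 on baseline, so the ANCOVA residual variance is 3² − (1 − b)² × SDbase². Estimating the slope with 46 completers multiplies this by 1 + 1/42. The variance ratio to the unadjusted change score is

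[1 − (1 − b)² × SDbase²/9] × 43/42.

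Example, b = 0.5 and SDbase = 2.0: (1 − 0.25 × 4/9) × 43/42 = 0.889 × 1.024 = 0.910.

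| Slope b | SDbase 2.0 | SDbase 2.5 | SDbase 2.89 |
|---|---|---|---|
| 0.5 | 0.910 | 0.846 | 0.787 |
| 0.6 | 0.951 | 0.910 | 0.872 |
| 0.8 | 1.006 | 0.995 | 0.986 |
| 0.9 | 1.019 | 1.017 | 1.014 |
| 1.0 | 1.024 | 1.024 | 1.024 |

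The ratio equals 1 at b = 1 − √(9/43)/SDbase, which is 0.77, 0.82 and 0.84 for the three SDs. Above that slope the unadjusted test is slightly more precise.

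**4. Simulated power of ANCOVA, 23 per group (100,000 trials per cell; unadjusted 0.803–0.807 throughout).**

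| Slope b | SDbase 2.0 | SDbase 2.5 | SDbase 2.89 | Implied baseline-to-12-week correlation |
|---|---|---|---|---|
| 0.5 | 0.839 | 0.864 | 0.889 | 0.33–0.48 |
| 0.6 | 0.825 | 0.842 | 0.855 | 0.38–0.53 |
| 0.8 | 0.802 | 0.805 | 0.809 | 0.47–0.62 |
| 0.9 | 0.796 | 0.797 | 0.799 | 0.52–0.66 |
| 1.0 | 0.797 | 0.795 | 0.795 | – |

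Type I error at b = 0.6 and 0.9 was 0.049–0.051 unadjusted and 0.048–0.051 adjusted.

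**5. Scale.** On the log scale, with effect 0.17 and SD of log change 0.20, adjusted power agrees with the table within 0.005 in every cell. If instead percent change (17%, SD 20%) is unrelated to baseline, the results are:

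- percent change, unadjusted: 0.805
- percent change with baseline added: 0.795
- ANCOVA in ml/kg/min on the same data: 0.788, 0.786 and 0.782 for the three baseline SDs

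The scale therefore has to be fixed together with the covariate.

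**The case against.** The strongest case against is that nothing is wrong with the planned test and that the sign of the benefit is unknown. The documents give no mean baseline, baseline SD or slope, and nothing in them places the slope below the break-even of 0.77–0.84. The largest gain (0.889) needs the most favourable cell. The entry range limits baseline spread and so limits what adjustment can recover. This also weakens a simpler calculation: the usual ratio (1 + ρ)/2 gives power of 81–90% for correlations of 0.95 to 0.5, but it assumes equal SDs at both times. With an SD of change of 3, a correlation of 0.9 would then need a baseline SD of 3/√(2 × 0.1) = 6.7, and no distribution on 10–20 can have an SD above 5.

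The natural reading of the sizing is percent change, and on that scale adjustment may lose about 0.01. A log-scale analysis estimates a ratio of geometric means, so its match to a difference in mean percent changes is approximate. Power is already 0.82 at the expected 24 completers. The regression on post-randomization variables is introduced as exploratory.

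All of this stands as a limit on the size of the gain. It does not show that the plan names a covariate or fixes a scale: a percent figure used for sizing suggests the analysis scale without prespecifying it. Within the ranges shown, the possible gain (up to about 0.08) is larger than the possible loss (about 0.01 on a matching scale). The case for naming one model on one scale does not depend on the slope.

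**Conclusion.** The point holds as a conditional loss of efficiency together with incomplete specification of the primary analysis. The sample size is not wrong and the design is not underpowered on its own assumptions.

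Under the assumptions listed, baseline adjustment at 23 completers per group adds about 2 to 8 percentage points of power at slopes of 0.5–0.6. It makes almost no difference at 0.8 and costs up to about 1 point at 0.9–1. If percent change is unrelated to baseline, an ANCOVA in ml/kg/min would cost about 2 points. Confidence in the textual facts is high. Confidence in the size of the gain is moderate at best, because the slope and the baseline SD are assumed. The change is worth making because it is cheap; it does not repair a flaw in validity.

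**What to change.** In the Statistical analysis plan:

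1. Prespecify the primary analysis as ANCOVA of 12-week peak VO2 on randomized group and baseline peak VO2.
2. Fix one scale in advance. Log peak VO2, for both outcome and covariate, would correspond closely to the percent effect used in the sizing; state that the estimate is then a ratio of geometric means.
3. Keep the unadjusted comparison of change as a sensitivity analysis, and leave the sample size as it is.
4. State that the regression on compliance and on changes in strength and muscle mass is exploratory and is not the test of the primary outcome.

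The two predictors fit within the plan's limit of four. No extra patients, visits or measurements are needed. The cost is one error degree of freedom (44 to 43 with 46 completers) and about 0.01 of power if the slope on the chosen scale is near 1.
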